5.3.5.6 Abnormal Vital Sign Values

Not every vital sign abnormality qualifies as an adverse event. A vital sign result must be reported as an adverse event if it meets any of the following criteria:

- Is accompanied by clinical symptoms
- Results in a change in study treatment (e.g., dosage modification, treatment interruption, or treatment discontinuation)
- Results in a medical intervention or a change in concomitant therapy
- Is clinically significant in the investigator's judgment

It is the investigator's responsibility to review all vital sign findings. Medical and scientific judgment should be exercised in deciding whether an isolated vital sign abnormality should be classified as an adverse event.

If a clinically significant vital sign abnormality is a sign of a disease or syndrome (e.g., high blood pressure), only the diagnosis (i.e., hypertension) should be recorded on the Adverse Event eCRF.

Observations of the same clinically significant vital sign abnormality from visit to visit should only be recorded once on the Adverse Event eCRF (see Section 5.3.5.4 for details on recording persistent adverse events).

5.3.5.7 Abnormal Liver Function Tests

The finding of an elevated ALT or AST ($>3 \times \text{ULN}$) in combination with either an elevated total bilirubin ($>2 \times \text{ULN}$) or clinical jaundice in the absence of cholestasis or other causes of hyperbilirubinemia is considered to be an indicator of severe liver injury (as defined by Hy's Law). Therefore, investigators must report as an adverse event the occurrence of either of the following:

- Treatment-emergent ALT or AST $> 3 \times \text{ULN}$ in combination with total bilirubin $> 2 \times \text{ULN}$
- Treatment-emergent ALT or AST $> 3 \times \text{ULN}$ in combination with clinical jaundice

The most appropriate diagnosis or (if a diagnosis cannot be established) the abnormal laboratory values should be recorded on the Adverse Event eCRF (see Section 5.3.5.2) and reported to the Sponsor immediately (i.e., no more than 24 hours after learning of the event), either as a serious adverse event or an adverse event of special interest (see Section 5.4.2).

5.3.5.8 Deaths

All deaths that occur during the protocol-specified adverse event reporting period (see Section 5.3.1), regardless of relationship to study drug, must be recorded on the Adverse Event eCRF and immediately reported to the Sponsor (see Section 5.4.2). This includes death attributed to progression of HD.

Death should be considered an outcome and not a distinct event. The event or condition that caused or contributed to the fatal outcome should be recorded as the single medical concept on the Adverse Event eCRF. Generally, only one such event should be reported. If the cause of death is unknown and cannot be ascertained at the time of reporting, "**unexplained death**" should be recorded on the Adverse Event eCRF. If the cause of death later becomes available (e.g., after autopsy), "unexplained death" should be replaced by the established cause of death. The term "**sudden death**" should not be used unless combined with the presumed cause of death (e.g., "sudden cardiac death").

If the death is attributed solely to progression of HD, "Huntington's disease progression" should be recorded on the Adverse Event eCRF.

Deaths that occur after the adverse event reporting period should be reported as described in Section 5.6.

5.3.5.9 Preexisting Medical Conditions

A preexisting medical condition is one that is present at the screening visit for this study. Such conditions should be recorded on the General Medical History and Baseline Conditions eCRF.

A preexisting medical condition should be recorded as an adverse event only if the frequency, severity, or character of the condition worsens during the study. When recording such events on the Adverse Event eCRF, it is important to convey the concept that the preexisting condition has changed by including applicable descriptors (e.g., "more frequent headaches").

5.3.5.10 Lack of Efficacy or Worsening of Huntington's Disease

Events that are clearly consistent with the expected pattern of progression of the underlying disease should not be recorded as adverse events. These data will be captured as efficacy assessment data only. If there is any uncertainty as to whether an event is due to disease progression, it should be reported as an adverse event.

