A pre-planned review of safety and efficacy data from Study BN40423, as well as available open-label data, was conducted by the BN40423 independent Data Monitoring Committee (iDMC). Following review of the data, the iDMC recommended that all dosing (120 mg Q8W and Q16W and placebo) in Study BN40423 be stopped. This iDMC recommendation was not based on any new emergent safety concerns, but on a totality of evidence indicating that the treatment arms demonstrated unfavorable safety and efficacy trends compared to the placebo arm over time. The iDMC also made a recommendation for the ongoing patients in the Study BN40423 to be followed for safety and efficacy outcomes as per protocol, without study drug administration.

As a result of iDMC's recommendation and Sponsor's decision, effective 22 March 2021, no further study treatment will be administered in this study. Patients on the study will continue to be followed for safety and efficacy outcomes until study completion (see Section 3.1.1.1, [Appendix 1a](#), and [Appendix 1b](#)).

The known potential risks related to lumbar punctures are elaborated, along with mitigation measures, in Section 5.1.

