5.3.5.11 Hospitalization or Prolonged Hospitalization

Any adverse event that results in hospitalization (i.e., inpatient admission to a hospital) or prolonged hospitalization should be documented and reported as a serious adverse event (per the definition of serious adverse event in Section 5.2.2), except as outlined below.

An event that leads to hospitalization under the following circumstances should not be reported as an adverse event or a serious adverse event:

- Hospitalization for respite care
- Planned hospitalization required by the protocol
- Hospitalization for a preexisting condition, provided that all of the following criteria are met:

The hospitalization was planned prior to the study or was scheduled during the study when elective surgery became necessary because of the expected normal progression of the disease.

The patient has not experienced an adverse event.

An event that leads to hospitalization under the following circumstances is not considered to be a serious adverse event, but should be reported as an adverse event instead:

- Hospitalization that was necessary because of patient requirement for outpatient care outside of normal outpatient clinic operating hours

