^l Urinalysis includes dipstick (pH, specific gravity, glucose, protein, ketones, blood) and microscopic examination for all abnormal dipstick results (sediment, RBCs, WBCs, casts, crystals, epithelial cells, bacteria).

^m The MRI should be scheduled to occur before the lumbar puncture. The MRI scan should be performed 7–14 days prior to the lumbar puncture to allow time for re-scanning if the quality of the initial MRI is inadequate. If the re-scan cannot be performed prior to the lumbar puncture, then it can be conducted the day after the lumbar puncture, as long as there are no post-lumbar puncture contraindications and it occurs within 2 weeks of the original scan.

ⁿ The C-SSRS will be used to monitor the patients (follow-up version, requiring approximately 5 minutes to administer, assuming absence of suicidal ideation and no change in clinical status from previous administration).

^o The cUHDRS is a composite motor, cognitive, and global functional clinical outcome measure in patients with HD comprised of the TFC, the TMS, the SDMT, and the SWR scores.

^p The electronic devices for remote data collection will be supplied to patients at screening and must be returned to the clinic in cases where the patient does not meet eligibility criteria, at the end of the study, or upon early termination from the study.

^q Optional exit interviews will be conducted for patients who consent from the selected sites within approximately 1 week after the EoT for ETT visit; these interviews can be conducted by telephone but may be completed by an in-clinic videotaped session.

^r Not applicable for a site that has not been granted approval for RBR sampling. Performed only for patients at participating sites who have provided written informed consent to participate.

Appendix 1b: Schedule of Activities for Early Treatment Termination (Applicable to all Patients from 22 March 2021) (cont.)

- ^s An interval medical history should be obtained at each clinic visit and safety telephone call and any changes in medications, any major procedures or hospitalizations, and any physician visits for HD or general medical care should be recorded.*
- ^t CSF samples will be obtained at the Week 101 EoT for ETT, and ETT visits but no study drug will be administered.*

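### Non-fatal serious events judged clearly to be HD progression are kept out of the adverse event data, and no endpoint counts them

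*Protocol*

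**What the plan says.** Section 5.3.5.10 sets the rule: "Events that are clearly consistent with the expected pattern of progression of the underlying disease should not be recorded as adverse events". It then says where they go: "These data will be captured as efficacy assessment data only". It also sets a limit: "If there is any uncertainty as to whether an event is due to disease progression, it should be reported as an adverse event". Serious non-fatal events are not treated separately.

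Section 5.3.5.11 classes an admission as serious when an adverse event led to it: "Any adverse event that results in hospitalization (i.e., inpatient admission to a hospital) or prolonged hospitalization should be documented and reported". Its exemptions are respite care, stays required by the protocol, and stays for a preexisting condition that were planned before the study or arose from elective surgery made necessary by expected progression, provided the patient has had no adverse event.

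Section 5.3.5.8 requires every death in the reporting period to be recorded on the Adverse Event eCRF and reported immediately: "This includes death attributed to progression of HD". A death due solely to HD is entered under the term Huntington's disease progression.

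Appendix 1a (footnote w) and Appendix 1b (footnote s) require an interval medical history at visits and safety calls, in which "any major procedures or hospitalizations, and any physician visits for HD or general medical care should be recorded".

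**The concern.** An acute admission or life-threatening deterioration that the investigator confidently puts down to HD is not an adverse event, so it cannot become a serious one. It is said to be held in the efficacy data, but those data are scale scores and responder proportions, and an admission has no place in them. The serious-event comparison between arms therefore depends partly on how each investigator attributes the event.

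This matters more than usual here. Section 1.3 reports that "the treatment arms demonstrated unfavorable safety and efficacy trends compared to the placebo arm over time", and patients are now being followed off drug for safety and efficacy outcomes. If active drug speeds decline, some of its serious consequences could look like the disease itself. The same section says the recommendation did not rest on any new emergent safety concern, so this is a question the follow-up should be able to answer, not an established harm.

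**Working it through.** The plan states no figure on this point and no rates from which one could be computed. The check sets the sections side by side.

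1. **The gate.** Section 5.2.1 includes worsening of an existing disease in the adverse event definition but refers to 5.3.5.10 for its application. Section 5.2.2 defines a serious adverse event as an adverse event that meets a seriousness criterion, and 5.3.5.11 and 5.4.2.2 build on the same term. An event classed as clear progression under 5.3.5.10 is therefore not an adverse event, not a serious one, not immediately reportable, and not in the adverse event summaries of Section 6.7.

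2. **The stated destination.** The endpoints in Sections 2.1.1 to 2.1.3 are changes in scale scores or sensor measures and proportions crossing a threshold on the TFC, cUHDRS or CGI-C. In Section 2.2, MoCA is a score and the C-SSRS covers only suicidal ideation and behavior. The one endpoint that counts serious clinical events generally is adverse event incidence, from which these events are excluded. For admissions and other serious events, the statement that they are captured as efficacy data is not met.

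3. **Against the rule for deaths.** Fatal progression has a recording route and a term (5.3.5.8). Non-fatal serious progression has neither.

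4. **Against the hospitalization exemptions.** Section 5.3.5.11 lists what is exempt, and acute admission for HD is not on the list. Its only mention of progression concerns elective surgery. A site reading 5.3.5.11 alone could report an acute HD admission that 5.3.5.10 tells it not to record.

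5. **Against the examination rules.** Section 4.5.3 excludes HD-related clinical progression when new or worsened findings are recorded as adverse events. The corresponding footnotes (Appendix 1a, i and j; Appendix 1b, e and f) carry no such exclusion.

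6. **What is still collected.** Hospitalizations are recorded under footnotes w and s whatever their cause. Two limits apply. The footnotes ask for no reason for admission, and the matching sentence in Section 4.5.2 mentions medication changes and physician visits but not hospitalizations.

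7. **Effect on the contrast.** In each arm, let S be the proportion of patients with a recorded serious event, and b the proportion whose only serious events were classed as clear progression. The full risk difference is (S_active + b_active) − (S_placebo + b_placebo). The recorded one is S_active − S_placebo. The part lost is b_active − b_placebo. It is zero if such events are equally common in the arms, and it hides excess harm only if they are more common on active drug. The protocol gives no value for either b.

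**The case against.** The strongest reply is that the bar is narrow. It covers only events clearly in line with the expected course, and any doubt sends the event to adverse event reporting. Faster-than-expected decline is arguably not the expected pattern. That stands as a limit on the loss, but it does not help where an investigator is confident and wrong.

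A reader might infer that hydrocephalus would be hidden, since its signs in Table 3 (gait, cognition, continence) resemble HD. The documents do not support that. Table 3 sends suspected cases to diagnostic work-up, a case under work-up is uncertain and so reportable, and Section 5.1.2.6 shows that hydrocephalus events have been reported in this study.

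A reader might also infer that serious worsening on active drug is missing from the comparison altogether. It is not. Decline is compared by arm on the cUHDRS, TFC, TMS and CGI, MoCA and C-SSRS are safety endpoints, and the iDMC reviews any relevant safety information unblinded (Section 3.1.2). What is missing is the count of these events as adverse or serious adverse events.

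The lack of a named hospitalization table in Section 6.7 is not an error in itself. The list there is not exhaustive, and such detail commonly sits in the SAP. But an SAP cannot restore to the adverse event data what sites were told not to record there.

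Finally, changing the rule after dosing has ended makes ascertainment differ before and after the amendment. That stands, and the fix has to allow for it.

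**Conclusion.** The point holds in a limited form. Non-fatal serious events that an investigator judges clearly to be HD progression are absent from the adverse event and serious adverse event data, the efficacy data do not count them as Section 5.3.5.10 says, and that section does not fit with 5.3.5.8 and 5.3.5.11.

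The size is unknown. The protocol gives no rate of HD-related admissions or of other serious worsening, so any power or count would rest wholly on assumed rates. A reader might infer that the rule favors active drug. The documents do not show this: the rule applies to all arms, and Section 4.2 keeps sites and patients blinded. The serious-event contrast shrinks only on the assumption that active drug raises the frequency of events classed as clear progression.

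The change is worth making because the loss depends on attribution, it bears on the harm question left for follow-up, and the remedy is cheap. It does not affect the primary efficacy analysis.

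**What to change.** - **Section 5.3.5.10:** limit the exclusion to events that meet no Section 5.2.2 seriousness criterion. Record serious events attributed to HD on the Adverse Event eCRF under the term Huntington's disease progression, which 5.3.5.8 already uses for deaths.
- **Section 6.7:** show these events by arm on a separate line, so that other serious-event counts are not diluted, and split them into before and after the change because ascertainment differs.
- **Whole study:** tabulate all-cause hospitalizations by arm from the interval medical history (Appendix 1a footnote w, Appendix 1b footnote s). This does not depend on attribution. Without a recorded reason for admission, it cannot isolate admissions for HD worsening.
- **Reconcile:** 5.3.5.10 with 5.3.5.11; Section 4.5.3 with the examination footnotes in Appendices 1a and 1b; and the interval-history sentence in 4.5.2 with footnotes w and s.

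The cost is a short wording change, some additional serious event entries and one extra table.

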5.3.5.11 Hospitalization or Prolonged Hospitalization

Any adverse event that results in hospitalization (i.e., inpatient admission to a hospital) or prolonged hospitalization should be documented and reported as a serious adverse event (per the definition of serious adverse event in Section 5.2.2), except as outlined below.

An event that leads to hospitalization under the following circumstances should not be reported as an adverse event or a serious adverse event:

- Hospitalization for respite care
- Planned hospitalization required by the protocol
- Hospitalization for a preexisting condition, provided that all of the following criteria are met:

The hospitalization was planned prior to the study or was scheduled during the study when elective surgery became necessary because of the expected normal progression of the disease.

The patient has not experienced an adverse event.

An event that leads to hospitalization under the following circumstances is not considered to be a serious adverse event, but should be reported as an adverse event instead:

- Hospitalization that was necessary because of patient requirement for outpatient care outside of normal outpatient clinic operating hours

5.3.5.12 Reporting Requirements for Cases of Accidental Overdose or Medication Error

Accidental overdose and medication error (hereafter collectively referred to as "special situations"), are defined as follows:

- Accidental overdose: accidental administration of a drug in a quantity that is higher than the assigned dose
- Medication error: accidental deviation in the administration of a drug

In some cases, a medication error may be intercepted prior to administration of the drug.

Special situations are not in themselves adverse events, but may result in adverse events. Each adverse event associated with a special situation should be recorded separately on the Adverse Event eCRF. If the associated adverse event fulfills seriousness criteria, the event should be reported to the Sponsor immediately (i.e., no more than 24 hours after learning of the event; see Section 5.4.2). For RO7234292 or placebo, adverse events associated with special situations should be recorded as described below for each situation:

- Accidental overdose: Enter the adverse event term. Check the "Accidental overdose" and "Medication error" boxes.
- Medication error that does not qualify as an overdose: Enter the adverse event term. Check the "Medication error" box.
- Medication error that qualifies as an overdose: Enter the adverse event term. Check the "Accidental overdose" and "Medication error" boxes.

In addition, all special situations associated with RO7234292 or placebo, regardless of whether they result in an adverse event, should be recorded on the Adverse Event eCRF as described below:

- Accidental overdose: Enter the drug name and "accidental overdose" as the event term. Check the "Accidental overdose" and "Medication error" boxes.
- Medication error that does not qualify as an overdose: Enter the name of the drug administered and a description of the error (e.g., wrong dose administered, wrong dosing schedule, incorrect route of administration, wrong drug, expired drug administered) as the event term. Check the "Medication error" box.
- Medication error that qualifies as an overdose: Enter the drug name and "accidental overdose" as the event term. Check the "Accidental overdose" and "Medication error" boxes. Enter a description of the error in the additional case details.
- Intercepted medication error: Enter the drug name and "intercepted medication error" as the event term. Check the "Medication error" box. Enter a description of the error in the additional case details.

As an example, an accidental overdose that resulted in a headache would require two entries on the Adverse Event eCRF, one entry to report the accidental overdose and one

entry to report the headache. The "Accidental overdose" and "Medication error" boxes would need to be checked on both eCRF pages.

5.3.5.13 Patient-Reported or Observer-Reported Outcome Data

Adverse event reports will not be derived by the Sponsor from PRO, ObsRO, or digital wearable device (HD mobile app) data, and safety analyses will not be performed using PRO or ObsRO or digital wearable device data. Sites are not expected to review the PRO or ObsRO or digital wearable device data for adverse events.

5.3.5.14 Safety Biomarker Data

Adverse event reports will not be derived from safety biomarker data by the Sponsor, and safety biomarker data will not be included in the formal safety analyses for this study. In addition, safety biomarker data will not inform decisions on patient management.

5.4 IMMEDIATE REPORTING REQUIREMENTS FROM INVESTIGATOR TO SPONSOR

Certain events require immediate reporting to allow the Sponsor to take appropriate measures to address potential new risks in a clinical trial. The investigator must report such events to the Sponsor immediately; under no circumstances should reporting take place more than 24 hours after the investigator learns of the event. The following is a list of events that the investigator must report to the Sponsor within 24 hours after learning of the event, regardless of relationship to study drug:

- Serious adverse events (defined in Section 5.2.2; see Section 5.4.2 for details on reporting requirements)
- Adverse events of special interest (defined in Section 5.2.3; see Section 5.4.2 for details on reporting requirements)
- Pregnancies (see Section 5.4.3 for details on reporting requirements)

The investigator must report new significant follow-up information for these events to the Sponsor immediately (i.e., no more than 24 hours after becoming aware of the information). New significant information includes the following:

- New signs or symptoms or a change in the diagnosis
- Significant new diagnostic test results
- Change in causality based on new information
- Change in the event's outcome, including recovery
- Additional narrative information on the clinical course of the event

Investigators must also comply with local requirements for reporting serious adverse events to the local health authority and IRB/EC.

